## 6.3 Visit 1: Screening Visit

A Screening Visit will take place up to 45 days prior to the Enrollment Visit. The study team will explain the procedures for the Phase I Safety and Acceptability Trial, and answer questions from prospective participants.

At this visit, YMSM ( $n\approx48$ ) will be consented to participate in Screening Procedures, which includes HIV/STI testing, and a brief, online survey regarding their sexual behaviors, prior experiences and comfort using rectal products, and douching or other rectal hygiene practices. Only participants who consent to participating in the Phase I trial will then undergo a medical exam. It is important to underscore that participants receive risk reduction counseling as part of both screening and enrollment procedures, including condoms and lube and discussion with site staff about daily oral PrEP.

YMSM who are <18 years old must be accompanied by a parent/guardian at this visit. Written informed consent will be obtained at the screening before any procedures are initiated. For participants who do not meet the eligibility criteria, screening will be discontinued once ineligibility is determined. Participants not meeting the eligibility criteria may be rescreened later, if appropriate, as in the case of a concomitant medication washout period. In such cases, the length of the washout period will be determined by the PI based on safety considerations and the elimination half-life of the concomitant medication. Screening labs may be repeated to determine eligibility.

- YMSM consenting and found to be evaluable for participation in the Phase I Trial (n≈16) will be scheduled for their Dosing visit once all HIV/STI labs have been confirmed, leaving no more than 45 days between the Screening and Baseline visits.
- YMSM not interested in enrolling or not eligible for enrollment in the Clinical Trial (n≈32) will be invited to participate in an online-facilitated in-depth interview (IDI) as part of the Screening visit (though not required to be completed on the same day as screening procedures). This interview will examine concerns, perceived barriers and challenges when invited to participate in a biomedical clinical trial to inform efforts focused on their engagement in future trials. The IDI will be conducted by a trained interviewer located at UPenn using video-conferencing.
- YMSM whose HIV tests are reactive will not be interviewed or be able to participate in the Phase I trial. The site staff will focus on linking these individuals to HIV-related care.

Component	Procedure/Analysis	
	

Obtain written informed consent

Assess eligibility

	
	Obtain demographic and locator information	
Administrative	
 
Provide counseling and condoms:         
 
HIV/STI risk reduction counseling
 
HIV pre- and post- test counseling
 
Provide a copy of pre- and post- visit reminders
 
Participant education: flexible sigmoidoscopy procedure with biopsy & rectal fluid collections
 
 
 
	
	Obtain complete medical history, documenting pre-existing conditions	
Clinical	
 
Review and record concomitant medications
 
Perform general physical exam
 
Obtain site laises, blood success (DD), beart sets (UD), terms seture (terms), beinkt
 
	
	• Obtain vital signs – blood pressure (BP), heart rate (HR), temperature (temp), height, and weight	
Safety Labs and STI Screening*: blood	
 
Collect blood specimens for:         
 
Complete Blood Count (CBC) with differential
 
Comprehensive Metabolic Panel (CMP), PO4
 
HBsAg
 
HIV-1antigen/antibody 4th generation testing (confirmatory tests as needed)
 
Syphilis testing (confirmatory test as needed)
 
 
 
	

#### The following activities (Table 8) will take place at the in-person screening visit: **Table 8: Visit 1 – Screening Visit**

Safety Labs and STI Screening*: urine and rectal	
 
Collect urine for toxicology screen
 
Collect urine sample for GC/CT (NAAT)
 
Collect rectal swab for GC/CT (NAAT)
 

	
 
Collect swab for HSV, if ulcerations are present on exam
 

Behavioral	• YMSM not interested in or not eligible for enrollment, In-depth interview regarding future participation in HIV biomedical trials

\*Screening laboratory values are valid up to 45 days.
6.4 Visit 2 - Enrollment Visit (Day 0)

Visit 2 must take place  $\leq$ 45 days after Visit 1. If more than 45 days pass before Visit 2, participants will need to be re-screened and re-consented. If deemed eligible based on the results from the screening procedures, participants will be contacted to schedule an Enrollment visit and asked to refrain from RAI and the insertion of anything in their anorectum for 72 hours prior to the visit. YMSM will complete a baseline web-survey examining questions on participants' prior experiences and comfort using rectal products, as well as douching or other rectal hygiene practices.

Baseline samples (see Appendix 1) will be collected to establish pre-dose conditions for safety assessments as well as sample collection for TFV analyte concentration in multiple matrices for participants taking oral TDF/FTC PrEP. Prior to proceeding to Visit 3 (Dosing Visit), the participant's plasma will be analyzed for tenofovir/emtricitabine. Individuals with quantifiable tenofovir/emtricitabine concentrations will be excluded from participation in the tenofovir douche administration and pharmacokinetic sampling. These concentrations will be used to adjust post-dose PK and PD assessments. The following activities (Table 9) will take place at the Enrollment visit:

Component	Procedure/Analysis
	Confirm participant understood and signed informed consent
	Review/update locator information
	Confirm eligibility
Administrative	• Ensure participant complied with pre-visit instructions
	
 
Provide counseling and condoms:         
 
HIV/STI risk reduction counseling
 
Provide a copy of pre- and post- visit reminders
 
Participant education: flexible sigmoidoscopy procedure with biopsy & rectal fluid collections
 
 
 

	Review/update medical history
	
 
Review/update incurcat instory
 
Review/update concomitant medications
 

	
 
Complete AE assessment
 

Clinical	
 
Review any available test results
 

	
 
Perform symptom-directed physical exam, including rectal exam, as needed
 

	
 
Collect vital signs (HR, BP, temp)
 

Safety Labs: blood	• HIV-1 antigen/antibody 4 th generation testing (confirmatory tests as needed)
Cleansing Enema	• Cleansing enema will be administered, in preparation for flexible sigmoidoscopy
Blood for PK, Plasma and PBMC	Plasma and PBMC's collected to measure baseline TFV/FTC concentrations
Rectal specimens for PD and Histology (Not conducted in participants < age 18; Prioritized for participants age 18 and above)	
 
COVID-19 sigmoidoscopy pre-screening per institutional policy
 
Perform flexible sigmoidoscopy with biopsy collection for explant evaluation/histology/banking
 

Behavioral	• Participant will complete Baseline Behavioral Survey Note: The Baseline Behavioral Survey may be completed at any time from the enrollment visit (Visit 2) until just prior to TFV douche dosing om Day 1 (Visit 3).

# Table 9: Visit 2 – Enrollment Visit

### 6.5 Visit 3 - Dosing Visit (Day 1)

Visit 3 must take place > 7 days and  $\leq$ 21 days after Visit 2 (the Enrollment Visit) and  $\leq$ 45 days from the Screening Visit 1. Prior to using the TFV douche, baseline samples (see Appendix 1) will be collected to establish pre-dose conditions for safety assessments as well as sample collection for TFV analyte concentration in multiple matrices for participants taking oral TDF/FTC PrEP. These concentrations will be used to adjust post-dose PK and PD assessments.

YMSM will then receive a dose of the TFV douche at the research unit, and, asked to retain the douche without defecation for 5 minutes, if possible. Subsequently, participants will be instructed on how to expel the douche contents. The amount of time that the douche was retained and the volume of expelled effluent will be measured. Post-dose observations and data collection will follow at 1, 6, 24 and 72 hours, using a sparse sampling design in which paired plasma and peripheral blood mononuclear cells (PBMC) are collected at all PK sampling times.

Participants are assigned to a single time point for flexible sigmoidoscopy with rectal biopsies at either 1,6, 24, or 72 hours after dosing (thus, providing 4 subjects at each time point). Anoscopy, with rectal fluid collection will occur pre-dose and at either 1, 6, 24, or 72 hours after dosing, coinciding with each participant's flexible sigmoidoscopy. Microbiome specimens will be collected via anoscopy pre-dose and at 24 hrs post-dose.

Between sampling windows, YMSM will complete a web-survey examining their perceived reactions and comfort using the study douche, factors influencing product use in the future, and comfort with the trial procedures. The survey will be administered after dosing, but scheduled not to interfere with other study assessments. Sampling for safety, PK, PD, and acceptability assessments will be collected according to a schedule of events (see Appendix 1). A summary of the proposed activities to take place at this visit is noted below:

Component	Procedure/Analysis
	Confirm participant understood and signed informed consent
	Review/update locator information
	Confirm eligibility
Administrative	• Ensure participant complied with pre-visit instructions
Aummistrative	
 
Provide counseling and condoms:
 

	
 
HIV/STI risk reduction counseling
 

	• Provide a copy of pre- and post- visit reminders
	• Participant education: flexible sigmoidoscopy procedure with biopsy (for participants assigned
	to 24 hr sampling) & rectal fluid collections
	Review/update medical history
	Review/update concomitant medications
Clinical	• Review any available test results
Chincar	• Perform symptom-directed physical exam, including rectal exam, as needed
	• Complete AE assessment
	• Collect vital signs (HR, BP, temp)
	Collect blood specimens for
	• CBC with differential
Safety Labs: blood	o CMP
	• HIV-1 antigen/antibody 4 th generation testing (confirmatory tests as needed)
	If indicated, syphilis (confirmatory tests as needed)
Safety Labs  : urine	• Collect urine sample for GC/CT (NAAT), if indicated
and rectal	• Collect rectal swab for GC/CT (NAAT), if indicated
	• Collect swab for HSV, if indicated
Study Product	Investigator or designated sub-investigator will administer study product to participants
Administration	
Blood for PK,	• Pre-Dose (within 30 min prior to dosing)
plasma, and PBMC	• Post-Dose:**
	$\circ$ 1 hr $\pm$ 15 min
Rectal Specimens:	$\circ$ 6 hr $\pm$ 60 min
Douche effluent	Collected to measure volume and TFV/FTC concentration
Rectal Specimens:	COVID-19 sigmoidoscopy pre-screening per institutional policy
Biopsies for PK/PD,	
histology	• Perform flexible sigmoidoscopy with biopsy collection at 1 hr ± 40 min, or 6 hr ± 40 min post-dose per each participant's designated specimen collection schedule **
(age 18 and above	per caen participant s'uesignated specifien concetion senedule
only)	
Rectal Specimens: Rectal Fluid for PK	Collect rectal swab for microbiome assessment
(Not conducted in	• Collect rectal fluid pre-dose for all participants and at 1 hr (± 15 min) or 6 hr (± 60 min) post-
participants < age 18;	dose per each participant's designated specimen collection schedule**
Prioritized for	
participants age 18	
and above)	
and Microbiome	
(collected in all	
participants)***	
Behavioral	Participant will complete Research Unit Dose Acceptability Questionnaire

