# 1.7 DREAM ATN Design Rationale

According to our working target product profile and our clinical niche as an on demand PrEP product, the TFV douche is being developed to provide protective concentrations in colon tissue cells for a similar duration as that achieved using the on demand oral F/TDF 2+1+1 regimen demonstrated equally effective with daily F/TDF in Ipergay. Therefore, sampling for PK and safety will occur over 72 hours based on our model-based PK estimates. In addition, we intend to establish the congruence of PK between adult in the DREAM studies and the YMSM population to be recruited in this DREAM ATN protocol. Accordingly, we propose a slightly shorter total PK sampling duration (3 days) when compared to DREAM-01 (7 days). This

will enable documentation of concentrations throughout the first day when DREAM-01 indicated sustained concentrations well above target concentrations in colon tissue cells as well as the initial decay in concentration that occurs between 24 and 72 hours when colon tissue TFV-DP median concentration falls nearer to the 4 dose per day target concentration.

To achieve these goals, blood (plasma and cells), colon tissue (tissue homogenate and cells), and rectal fluid will be collected using a relatively sparse sampling scheme that balances a desire for rich PK data collection and feasibility. Altogether, each participant will have 5 pharmacokinetic blood samples, 2 rectal fluid samples, and 2 biopsy sessions (up to eight pinch biopsies at baseline and 20 pinch biopsies at one time point following dosing) for the enema product studied. The total number of pinch biopsies collected following enema formulation dosing (n=20) in adolescents is well below the number collected in adult participants (n=120) in DREAM-01.

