## 9. STATISTICAL CONSIDERATIONS

#### 9.1 Overview and Summary of Design

This is an exploratory, open label study to compare the safety, PK, PD, and acceptability of the formulation of a TFV microbicide enema. The goal of the study is to describe the pharmacokinetic parameters in a population of a TFV douche currently under development in a population of young men who have sex with men (YMSM).

Eligible YMSM will be contacted by site staff to schedule an in-person Screening Visit at the ATN site. A Screening Visit will take place up to 45 days prior to the Baseline enrollment Visit. At this visit, YMSM ( $n\approx48$ ) will learn about the Phase I trial and be invited to participate in the study. All participants will be consented and those who agree to participate in the Phase 1 portion the study will complete Screening Procedures, which includes a medical exam, HIV/STI testing, and a brief, online survey regarding their sexual behaviors, prior experiences and comfort using rectal products, experiences and willingness to participate in the trial and scheduled for their PK/PD visit once all HIV/STI labs have been confirmed. YMSM who choose not to participate in the Phase I trial or who are ineligible to participate due to labs results ( $n\approx32$ ) will be invited to participate in an online-facilitated in-depth interview (IDI). The screening, enrollment, dosing, and termination visits will take place at Johns Hopkins University.

After completing the screening evaluation, we will enroll 16 evaluable participants. YMSM who are willing and cleared to participate in the Trial visit will be asked to use a single dose of a tenofovir (TFV) rectal microbicide douche (600mg TFV in 125mL 0.45% NaCl [half-normal saline]) at the Hopkins study site. Prior to using the TFV douche, baseline samples (see Appendix 1) will be collected to establish pre-dose conditions for safety assessments.

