## 16. APPENDICES

# **APPENDIX I: SCHEDULE OF STUDY VISITS AND EVALUATIONS**

		Screening Visit	Enrollment Visit	Dosing & Sampling Visits			Final/Early Termination Visit	Follow- up
Visit #		1	2	3	4	5	6	Phone Call
Visit Day			≤45 days from Screening	Day 1 >7d and ≤21 Days from Enrollment	Day 2 (24hrs)	Day 4 (72hrs)	Day 5 (+3 days) (96hrs)	if needed
ADMINISTR	RATIVE					•		
Informed con	isent	Χ						
Assessment o	f Eligibility	X	X	X	X	X	X	
Review Demo Locator Info		X	X	X	X	X	X	
Review and u Medical Histo		X	X	X	X	X	X	
Review Conc Medications	omitant	X	X	X	X	X	X	
AE Assessme	AE Assessment		Χ	X	Χ	X	X	
Query for Compliance with Pre-Visit Instructions			X	X	X	X	X	
Provide Pre/l Reminders	Provide Pre/Post Visit Reminders		X	X	X	X	X	
Review STI Risk Reduction Counseling & Provide Condoms		X	X	X	X	X	X	
Participant education: flexible sigmoidoscopy procedure with biopsy & rectal fluid collections		X	X	X	X	X		
Review lab re	esults		X	X	X	X	X	X
CLINICAL								
	Complete	Χ						
Physical Exam	Symptom- Directed		X	X	X	X	X	
	VS (BP, HR, Temp, HTC ‡ , Wt ‡ )	X	X	X	X	X	X	
Cleansing Enema			X			X		
SAFETY LA	BS							
Disci	CBC w/ Diff	X		X			X	
Blood	СМР	X		X			X	
	PO4	Χ						

	HBsAg	X						
Urine	Toxicology Screen ††	X						
ii		Screening Visit	Enrollment Visit	Dosing & Sampling Visits			Final/Early Termination Visit	Follow- up
Visit #		1	2	3	4	5	5	Phone Call
Visit Day			≤45 days from Screening	Day 1 >7d and ≤21 Days from Enrollment	Day 2 (24hrs)	Day 4 (72hrs)	Day 5 (96hrs)	If needed
STI TESTINO	Ĵ						•	
Blood	HIV Testing †	X	X	X			X	
DI000	Syphilis Testing †	X	$\mathbf{X}^{\dagger\dagger\dagger}$	$\mathbf{X}^{\dagger\dagger\dagger}$			$\mathbf{X}^{\dagger\dagger\dagger\dagger}$	
Urine	GC/CT NAAT	X	$\mathbf{X}^{\dagger\dagger\dagger\dagger}$	$\mathbf{X}^{\dagger\dagger\dagger\dagger}$			$\mathbf{X}^{\dagger\dagger\dagger}$	
Rectal Swab	GC/CT NAAT	X	$\mathbf{X}^{\dagger\dagger\dagger}$	$\mathbf{X}^{\dagger\dagger\dagger}$			$\mathbf{X}^{\dagger\dagger\dagger\dagger}$	
Swab	HSV PCR NAAT	X †††	X †††	X †††			X †††	
DOSING/STU	DY PRODUC	Т						
Study Product Administration				X				
STUDY SPEC	CIMEN COLL	ECTION ††††						
	Pre- dose		X	X				
Blood	1hr			X				
PK/PBMC 	6hr			Χ				
	24hr				X			
	72hr					X		
Rectal Biopsies *2 (Not conducted in participants < age 18; Prioritized for participants ≥18 years)	Pre- dose		X					
	d 1hr			X				

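### Enrollment is allowed up to day 45 after screening, but the dosing rule leaves no permitted dosing day for anyone enrolled on days 38 to 45, and Appendix I omits the dosing cap

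*Combined protocol and SAP*

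**What the plan says.** **Enrollment (Visit 2).** Section 6.3 states "A Screening Visit will take place up to 45 days prior to the Enrollment Visit", and section 9.1 repeats it: "A Screening Visit will take place up to 45 days prior to the Baseline enrollment Visit". The Visit 2 cell of Appendix I gives the same 45-day limit. Section 6.4 adds the only consequence for lateness: "If more than 45 days pass before Visit 2, participants will need to be re-screened and re-consented".

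**Dosing (Visit 3).** Section 6.5 begins "Visit 3 must take place > 7 days and" and sets two upper limits: 21 days after Visit 2, and 45 days from the Screening Visit. The Visit 3 cell of Appendix I reads only "Day 1 >7d and ≤21 Days from Enrollment", with no limit counted from screening.

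**Linked rules.**
- The footnote to Table 8 says "Screening laboratory values are valid up to 45 days".
- Section 6.4 requires that, before Visit 3, the participant's "plasma will be analyzed for tenofovir/emtricitabine"; a quantifiable result bars dosing.
- Baseline sigmoidoscopy with biopsies takes place at Visit 2 in participants aged 18 or over who have GI sampling (Table 9). Section 1.7 gives the number as "up to eight pinch biopsies at baseline", while a footnote to Appendix I says up to 5.

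**The concern.** A site can follow 6.4 to the letter and still enroll someone whom 6.5 does not allow it to dose. The re-screening rule in 6.4 does not help, because it starts only after day 45. Section 6.3 allows rescreening of people who fail eligibility, and repeat screening labs to settle eligibility. Neither provision expressly covers someone already enrolled, and neither resets the 45-day dosing cap.

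Three courses then remain: replace the participant, re-screen him without a stated rule, or dose him out of window. If he is an adult having GI sampling, he has already had a sigmoidoscopy whose biopsies will have no post-dose pair, although section 9.6 compares each post-dose explant result with the pre-dose baseline. Shortening the gap between Visits 2 and 3 is not a remedy, because section 5.7 advises against rectal insertion for 7 days after each biopsy session.

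The Appendix I omission carries a separate risk. A site scheduling from that table alone could dose after the screening labs have lapsed. CBC, CMP and HIV testing are repeated at Visit 3. Phosphate and HBsAg, both tied to exclusion criteria in 4.2, are scheduled only at screening, and the CMP defined in 6.14.1 does not include phosphate.

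**Working it through.** The plan gives no figure of its own to reproduce, so this is a direct count of days.

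**Inputs.** Put Visit 1 on day 0, Visit 2 on day d and Visit 3 on day v.
- d is at most 45 (6.3, 6.4, 9.1, Appendix I).
- v is more than d + 7, so at least d + 8 in whole days (6.5, Appendix I).
- v is at most d + 21 (6.5, Appendix I).
- v is at most 45 (6.5 only).

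**Permitted dosing days under 6.5.** Visit 3 may fall on days d + 8 to min(d + 21, 45). The number of days is

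min(d + 21, 45) − (d + 8) + 1 = min(14, 38 − d), and not below 0.

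| Visit 2 on day d | Permitted dosing days | Number |
|---|---|---|
| 24 | 32 to 45 | 14 |
| 25 | 33 to 45 | 13 |
| 31 | 39 to 45 | 7 |
| 36 | 44 to 45 | 2 |
| 37 | 45 | 1 |
| 38 | none (earliest would be 46) | 0 |
| 45 | none (earliest would be 53) | 0 |

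The full 14-day window is available for d up to 24 and then shrinks by one day per day. It is empty for d = 38 to 45, which is 45 − 38 + 1 = 8 calendar days.

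**Sensitivity to the reading of the lower limit.** In continuous time the boundary is the same: at d = 38, v would have to exceed 45 and also be at most 45. If the rule were read as at least 7 days, day 38 would become feasible and the empty range would be days 39 to 45. Section 6.5 and Appendix I both print a strict inequality.

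**Appendix I alone.** Without the 45-day cap, Visit 2 on day 38 allows dosing on days 46 to 59, and Visit 2 on day 45 allows days 53 to 66. The latest day is 45 + 21 = 66, which is 66 − 45 = 21 days past the validity of the screening labs.

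**The other way to reconcile the rules.** If Visit 2 is to stay allowed up to day 45, the dosing cap would have to be at least 45 + 8 = 53 days for one permitted day, or 45 + 21 = 66 days for the full window.

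**The case against.** The strongest reply is that the windows can be met together: 6.4 sets an outer limit, 6.5 adds a tighter one, and a coordinator obeying both would hold Visit 2 by day 37. Section 6.3 also ties the scheduling of dosing to confirmation of the HIV/STI labs, so an infeasible date could be spotted before any biopsy. There is one clinical site, and a study-specific procedures manual, which is not among the documents, might already set the limit. Appendix I is described in 6.1 as an overview, and reaching day 66 means ignoring both 6.5 and the Table 8 footnote. The HBsAg exclusion is worded as a screening result, so that criterion does not go unassessed when 45 days pass. Finally, only 16 participants are planned, replacement is allowed, and the number affected could be zero.

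Some of this stands. The frequency is unknown and may be nil, a careful site can avoid the problem, and the lapsed-lab point rests more on phosphate than on HBsAg. None of it removes the conflict. Four places state 45 days and none states 37. The only re-screening trigger written for a late Visit 2 starts at the wrong day. Repeating labs refreshes the results but does not lift the cap. The Appendix I note that excuses timing departures concerns specimen collection times, not visit windows.

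Late enrollment is also foreseeable: screening may take several visits (6.2), a positive COVID result cancels a visit until clearance (6.1), and section 4.3 expects some participants to need more time to enroll.

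**Conclusion.** The concern holds. Under the rules as written, Visit 2 on any of days 38 to 45 is permitted but leaves no permitted dosing day, and days 25 to 37 leave a shortened window. The Visit 3 cell of Appendix I lacks the cap that 6.5 imposes.

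The eight days are calendar days, not a predicted share of participants; the documents give no distribution of Visit 2 timing. Sample size, power and type I error do not change, and four participants per biopsy time can be kept through replacement (4.4, 6.10, 9.7). What is at stake is an avoidable sigmoidoscopy with unpaired baseline biopsies and one more recruit for each affected participant, or else a dose outside the window. The day-38 boundary rests on the strict reading of the 7-day gap. The change should be made, as a matter of schedule consistency and participant burden.

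**What to change.** 1. Limit Visit 2 to at most 37 days after Visit 1 in 6.3, 6.4, 9.1 and the Visit 2 cell of Appendix I, and move the re-screening trigger in 6.4 to match.
2. Preferably set the limit earlier, since day 37 leaves a single dosing day and dosing must wait for the Visit 2 plasma result. Day 31, for example, leaves seven. The choice should follow the laboratory's turnaround time, which the documents do not give.
3. Add a limit of 45 days from screening to the Visit 3 cell of Appendix I.

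Lengthening the dosing cap to between 53 and 66 days would also reconcile the rules. It would take dosing beyond the validity of the screening labs, so phosphate at least would need repeating before dosing.

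The cost is one number in four places, one phrase in Appendix I, the usual amendment approval and registration, and slightly less scheduling freedom for the site. No endpoint, sample size or analysis changes.
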